5.4 Withdrawal of individual subjects

Subjects can leave the study at any time for any reason if they wish to do so without any consequences. The investigator can decide to withdraw a subject from the study for urgent medical reasons.

5.5 Premature termination of the study

The only reason to end the study prematurely is because we can't get enough participants. If this is the case, we will use the gathered data for a brief report.

6. SAFETY REPORTING

6.1 Temporary halt for reasons of subject safety

This is not applicable because it is a retrospective observational study with one moment of data collection.

6.2 AEs, SAEs and SUSARs

This is not applicable because it is a retrospective observational study with one moment of data collection.

6.3 Annual safety report

N.a.

6.4 Follow-up of adverse events

N.a.

6.5 [Data Safety Monitoring Board (DSMB) / Safety Committee]

The data were gathered in routine treatment procedures. For the purpose of the study, after merging several sources in full database case numbers were anonymized in a way no cases could be traced back. Fully anonymized and corrected data were handed over to the research team. The authors assert that all procedures contributing to this work comply with the ethical standards of the relevant national and institutional committees on human experimentation and with the Helsinki Declaration of 1975, as revised in 2008. The Ethical Commission of the Radboud University, Social Sciences, the Netherlands, reviewed the procedure used in this study and decided that, because no actions or behaviours are imposed on the participants, there was no need for further ethical review.

STATISTICAL ANALYSIS

This study will not test any intervention. It will focus on the level of agreement between patients responses on the newly used instrument for screening and brief assessment of addiction problems (TAPS/TAPS-ID) and the golden standard (MATE / SumID-Q).

Research goal 1:

- With regard to the reliability of the TAPS, the internal consistency is determined (Cronbach's alpha and item-total correlation). To determine the convergent validity, first the correlation is determined between the outcome of the TAPS (indications of problematic use) and the outcome of the severity of the addiction on the MATE (degree of severity).
- To investigate the influence of addiction problems on treatment outcomes and quality of life, the correlation with the outcomes of the Honos and Mansa is calculated. The hypothesis is that a higher score on the TAPS correlates with a higher score on the Honos and a lower score on the Mansa.
- The optimal cut-off point of the TAPS is determined by means of ROC analyses.

Research goal 2:

- For the development of the TAPS-ID, the feasibility (by the interviewers) and feasibility (with the target group) will first be estimated on the basis of a few interviews with the interviewers involved.
- With regard to the reliability of the TAPS, the internal consistency is determined (Cronbach's alpha and item-total correlation). To determine the convergent validity, the correlation is determined between the outcome of the TAPS and the outcome of the SumID-Q.

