3. STUDY DESIGN

This is a descriptive study based on routinely collected data. The FACT teams that participate in the study work according to a care program in which screening and assessment are part of the standard care. This implies that since 2016, screening has been carried out at the start of treatment for: PTSD, a mild intellectual disability, addiction problems. The current screening for addiction problems is too limited and lacks a follow-up step in the form of structured assessment. In addition, at the start of treatment and annually in preparation of the treatment plan, the level of complaints is assessed by the care provider involved and the phase of recovery and the patient's quality of life are assessed. We want to use this data from patients in whom there is no suspicion of mild intellectual disability in anonymised form. In the research into the validity of the TAPS, we want to measure whether there is a relationship between the existence of problem substance use and a poorer treatment outcome (less decrease in complaints), and a reduced quality of life.

The TAPS has already been included as a replacement for the previously used screener for addiction problems by the various substantive advisory bodies that deal with the content and improvement of the care of the GGZ Oost Brabant.

In order to investigate the concurrent validity of the TAPS, a group of at least 40 patients will be asked permission to administer some parts of the MATE in addition to the TAPS.

The TAPS is too difficult for patients with intellectual disabilities. We therefore made adjustments to the translated TAPS (see below). The adjusted version for patients with ID is called the TAPS-ID. The validity of the TAPS-ID is examined by the comparison of the TAPS-ID and the SumID-Q (an instrument specially developed to map addiction problems in patients with MID). This will be carried out in a special department within secondary healthcare for patients with a combination of a severe mental disorder and intellectual disability (LVB-P) and in a healthcare setting for people with intellectual disabilities with minimal or light mental disorders (ORO). The SumID-Q is part of standard care for both departments. Trained employees who administer the SumID-Q also take the TAPS-ID.

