We would like to analyze the results of these measurements retrospectively over a period of at least 6 months by placing them anonymously and not traceable to individual persons in an SPSS database. We would also like to add some very global background data to this, namely: sex, age in years and the main psychiatric diagnosis. This data will be added to the database without name or other personally identifiable information by a secretary who is affiliated with the research line and who has access to this data in that regard. For this

reason, this secretary also has temporary access to the secured data from the electronic patient file.

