Participants were invited by telephone for the regular appointment that was scheduled at least one day later. During this telephone conversation, information was given about the validation study of the TAPS and patients were asked if they want to think about voluntarily participation. During the appointment, the information about the validation study was reviewed again, any additional questions from the patients were answered and when the patient agreed for participation, informed consent was signed. Patients signed informed consent to use the answers of the TAPS and MATE and background information (age, gender, diagnosis, medication, level of education) anonymously for this scientific purpose.

To investigate research objective 1, the following measuring instruments are used:

TAPS:

Tobacco, Alcohol, Prescription medication and other Substances-tool.

The TAPS-tool is a 2-phase screening instrument to detect substance use problems which can be used as an interview or as a self-administered questionnaire. According to McNeely et al., the diagnostic characteristics of both ways are similar (McNeely et al., 2016).

The TAPS-1 (screener) pretends to detect unhealthy substance use in the past year quickly and is based on NIDA's quickscreen. It contains of four multiple choice questions where the patient answers how often they used tobacco, alcohol, other drugs, and prescription medication in te past year on a five point Likert-scale.

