6.6 Primary study parameter(s)

Statistical analysis will examine agreement between different measures of substance use (sensitivity, specificity and AUC value) to evaluate the level of classification accuracy for each items or candidate combination of items.

This study will not include follow up assessments. We expect a number of patients who don't want the assessment at all or don't want to sign informed consent. The extent of missing data will be analyzed and explore differences in missing data by age, gender, and diagnosis.

On objective 1 the primary study parameters are TAPS and MATE outcomes. The total TAPS-score is used as

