6.7 Secondary study parameter(s)

The analysis of size and content of addiction problems will be done by an overview of descriptive statistics of the whole patient population, sorted by different substances being used.

For objective 1 the correlation with quality of life (MANSA) and amount of mental complains and social functioning (HoNOS) is also calculated for the divergent validity.

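### The unadjusted TAPS correlations with HoNOS and MANSA suit the validity purpose but cannot be read as influence; an estimate adjusted for age, sex and diagnosis should stand beside them

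*Combined protocol and SAP*

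**What the plan says.** The Statistical Analysis, Research goal 1, states the aim and the method in one sentence, which begins: "To investigate the influence of addiction problems on treatment outcomes and quality of life, the correlation with the outcomes of the Honos and Mansa". The next sentence gives the hypothesis: "The hypothesis is that a higher score on the TAPS correlates with a higher score on the Honos and a lower score on the Mansa". Neither sentence names a covariate, and no partial correlation, regression or stratification appears elsewhere in the document.

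The same analysis is described differently in two other places. Section 6.7 lists the correlation with MANSA and HoNOS as secondary and says that it "is also calculated for the divergent validity". Section 3 places it within the research into the validity of the TAPS and asks about "a relationship between the existence of problem substance use and a poorer treatment outcome (less decrease in complaints", and about reduced quality of life.

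The background variables in the database are "sex, age in years and the main psychiatric diagnosis" (section 3). The consent paragraph in section 5.3 also lists medication and level of education. The only analysis that uses any of these variables is in section 6.6, which will "explore differences in missing data by age, gender, and diagnosis".

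**The concern.** A question about influence is to be answered with a correlation for which no adjustment is planned. Section 1 gives a reason to expect confounding: it says that the risk of addiction problems rises with the severity of the psychiatric condition. HoNOS is described in section 5.3 as reflecting mental and social functioning. On the plan's own premises, then, the psychiatric condition is related to both scores. A diagnosis group with more substance use and also higher HoNOS scores would produce a correlation without any contribution from addiction itself. A confounder acting in opposite directions on the two scores could hide a real association.

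What is at stake is how a secondary result is interpreted. A correlation that partly reflects case mix could be published as an effect of addiction on outcome and quality of life, when the variables needed to check this are already held.

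**Working it through.** **Inputs from the documents.** The plan gives no expected correlation, significance level or power for this analysis. The one sample figure with its own inputs is in section 4.4, and it reproduces: 2.5 years × 100 new patients per year × (1 − 0.40) = 150 FACT patients without mild intellectual disability. The same section stops collection at 100 participants per group. The minimum of 40 in section 3 belongs to the MATE comparison. HoNOS and MANSA are part of the routine assessment, so 40 need not be the number for this correlation. I use n = 100 as the main case and n = 40 as the low end.

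**Assumptions.** There is one confounder, with the same correlation c (in absolute value) with the TAPS and with the outcome score. I vary c from 0.1 to 0.5, because the documents give no value. The example value for the observed correlation, 0.30, is also assumed. For MANSA the expected sign is negative and the arithmetic is the mirror image.

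**Formulas.**
- Adjusted value of an observed 0.30: (0.30 − c²) / (1 − c²).
- Raw correlation if nothing remains after adjustment: c².
- Raw correlation if the adjusted value is truly 0.30 and the confounder acts in opposite directions: 0.30 × (1 − c²) − c².

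| c | Observed 0.30 after adjustment | Raw r if adjusted r is 0 | Raw r if adjusted r is 0.30, opposite directions |
|---|---|---|---|
| 0.1 | 0.29/0.99 = 0.29 | 0.01 | 0.287 |
| 0.2 | 0.26/0.96 = 0.27 | 0.04 | 0.248 |
| 0.3 | 0.21/0.91 = 0.23 | 0.09 | 0.183 |
| 0.4 | 0.14/0.84 = 0.17 | 0.16 | 0.092 |
| 0.5 | 0.05/0.75 = 0.07 | 0.25 | −0.025 |

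**Against a 5% two-sided threshold** (my yardstick; the plan sets none). Critical r = t / √(n − 2 − k + t²), with k covariate terms. At n = 100 this is 0.197 for k = 0 and 0.202 for k = 5 (age, sex and three diagnosis indicators). Of the values in the table, only c = 0.4 and 0.5 take 0.30 below 0.202. At n = 40 the unadjusted critical value is 0.312, so 0.30 would not reach it even before adjustment. With no true adjusted association, the chance of p < 0.05 from case mix at n = 100 is 14%, 36% and 71% for c = 0.3, 0.4 and 0.5.

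**What adjustment costs.** The smallest correlation detectable with 80% power is tanh[(1.960 + 0.842) / √(n − k − 3)].
- n = 100: 0.277 for k = 0, 0.284 for k = 5.
- n = 40: 0.431 for k = 0, 0.458 for k = 5.

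For an estimate of 0.30, the 95% interval goes from 0.110–0.469 to 0.105–0.473 at n = 100, and from −0.013–0.559 to −0.037–0.576 at n = 40.

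**The case against.** The strongest reply is that one word carries the criticism. Section 6.7 gives the correlation a validity purpose, section 3 speaks of a relationship, and the hypothesis says only that the scores correlate. For construct validity a raw correlation is an acceptable statistic, even if part of it runs through diagnosis. This stands. A reader might infer that the planned correlation is the wrong analysis, and the documents do not support that.

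Second, the size is assumed. With c of 0.1 or 0.2 the estimate hardly moves, and at c = 0.3 it stays above the threshold at n = 100. A reader might infer that case mix will decide the result. The documents do not support that either: they give neither the size nor the direction of any confounding.

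Third, adjusting for main diagnosis is not clearly right. Diagnosis may overlap with the severity that HoNOS measures. If a substance use disorder can be the main diagnosis, which the documents do not say, adjustment would remove part of the TAPS signal. This stands, and it is why a result without diagnosis is also needed.

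Fourth, adjustment cannot turn the result into influence on treatment outcome. Section 3 defines a poorer outcome as a smaller decrease in complaints. Sections 6.1 and 6.2 describe one moment of data collection, and section 6.6 excludes follow-up assessments. This stands in full.

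What remains is that the aim, as written in the Statistical Analysis, goes beyond what its method can show, and a better-matched estimate is available from data already planned.

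**Conclusion.** The point holds in a limited form. The raw correlation may stay as validity evidence, but it should not be reported as influence. That no adjustment is planned is inferred from the absence of any named covariate; there is no explicit statement.

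Under the assumed range of c, an observed 0.30 would correspond to an adjusted value anywhere from 0.29 to 0.07. Weak confounding is negligible. Under the equal-correlation assumption, it takes about 0.4 or more with both scores to change the reading of 0.30 at n = 100. Which case applies cannot be known before the data are in, which is the reason to prespecify the adjusted estimate.

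A reader might go on to doubt the study's main validity results. The documents give no ground for that here: the comparison of the TAPS with the MATE, the sensitivity, specificity and AUC, and the cut-off all stand apart from this secondary correlation. Nor would an adjusted estimate establish an effect of addiction on treatment outcome.

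**What to change.** 1. In the Statistical Analysis, Research goal 1, replace influence by association, and specify the analysis along these lines:

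> The association of the TAPS score with the HoNOS and with the MANSA is reported as an unadjusted correlation and, beside it, as a partial correlation or linear regression estimate adjusted for age, sex and main diagnosis in a few broad groups, each with a 95% confidence interval. A sensitivity analysis omits diagnosis.

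2. State the diagnosis groups in advance, and say whether a substance use disorder can be the main diagnosis.

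3. Reconcile section 3, which defines treatment outcome as a change in complaints, with sections 6.1, 6.2 and 6.6, which describe a single measurement moment without follow-up. Word the aim to match whichever applies.

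The cost is a few lines of text and two extra estimates per scale; age, sex and diagnosis are already to be collected. The loss of precision is small at 100 patients. It is larger near 40, where diagnosis would need coarser grouping.

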Possible answers are: never, less than monthly, monthly, weekly, daily or almost daily. For tobacco and drugs, a positive score is given when there is any use in the past year. For alcohol a positive score is given when someone drinks more than 4 (women) or 5 (men) drinks containing alcohol a day. For medication, a positive score is obtained when someone uses prescription medication in a higher dose, or uses medication from someone else or medication without prescription. If there is a positive score on any of the sections, the TAPS-2 is assessed (see below). Dus de TAPS-1 levert geen scores op zichzelf op, maar de scores dienen ertoe om te beslissen of je doorgaat met de TAPS 2 of niet? For the TAPS-1, the optimal cut-off points for the detection of a possible substance use disorder (SUD) are: For tobacco and alcohol a frequency of monthly use was a predictor for SUD (sensitivity = 0.92 and 0.71, specificity = 0.80 and 0.85, AUC = 0.86 and 0.78, respectively) and for illicit drugs and prescription medication misuse any reported use was suspect for SUD (sensitivity = 0.93 and 0.89, specificity = 0.85 and 0.91, AUC = 0.89 and 0.90, respectively).

(Gryczynski et al., 2017)

TAPS-2 (brief risk assessment) is based on the ASSIST-lite (Alcohol, Smoking and Substance Involvement Screening Test) which is developed by the World Health Organization (Ali, Meena, Eastwood, Richards, & Marsden, 2013). The ASSIST has a

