good test-retest reliability: substance risk scores from two administrations within 1-4 weeks has excellent concordance (90–98%) and a high correlation (ICC 0.90–0.97) for tobacco, alcohol, and drugs (McNeely et al., 2014). The ASSIST-Lite (a shortened version of the ASSIST) has a single factor structure on which all substances loaded (eigenvalue range, 2.42–3.81). It also has a consistent pattern of positive loadings on this factor (all ≥ 0.303) (Ali et al., 2013). For the TAPS-2, only ADHD medication and questions about the failure to reduce or stop the use of marihuana, amphetamines and anxiolytics have been added to the ASSIST-Lite. There are nine categories on the TAPS-2: tobacco, alcohol, marihuana, stimulant drugs, opiates, anxiolytic medication, ADHD medication and 'other substances'. Only the elements with a positive score on the TAPS-1 are further assessed. For every category, the assessment with the TAPS-2 contains the usage for the last 3 months and two or three additional questions which can detect unhealthy use. For scoring both the use for the last 3 months and an affirmative answer on each of the additional questions lead to one point. A total score is calculated for each of the categories separately by adding the positive answers together. A total score of +2 per category induces a risk of a substance use disorder and indicates more assessment. Investigation of the TAPS-2 has been done by a comparison with the Composite International Diagnostic Interview (CIDI). Problematic use (with a cut off score of +1) for tobacco has a sensitivity of 0.93 and specificity of 0.87. Alcohol has a sensitivity of 0.74 and specificity of 0.79. For problematic use of illicit and prescription drugs, sensitivity ranges from 0.82 for marijuana to 0.63 for sedatives, and specificity is 0.93 or higher. For identifying any SUD, sensitivity was lower, but a cut off score of +2 greatly increases the likelihood of having a SUD as measured by the CIDI (McNeely et al., 2016).

HoNOS:

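### Goal 1: if sensitivity and specificity are reported at the ROC-derived TAPS cut-off in the same 40 to 100 patients, their sum is overstated on average under rules that maximise accuracy, and no internal validation is planned

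*Combined protocol and SAP*

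**What the plan says.** The Statistical Analysis text, Research goal 1, gives the cut-off one sentence: "The optimal cut-off point of the TAPS is determined by means of ROC analyses". No criterion follows. Section 6.6 names the accuracy measures: "Statistical analysis will examine agreement between different measures of substance use (sensitivity, specificity and AUC value". It applies them to single items or candidate combinations of items.

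Section 3 asks for at least 40 patients with both TAPS and MATE, and section 4.4 stops collection at 100 per group. Section 6.6 adds "This study will not include follow up assessments". No section mentions a second sample, a split sample, cross-validation, a bootstrap or confidence intervals.

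The only scoring rule is in section 5.3. For each substance category the TAPS-2 "contains the usage for the last 3 months and two or three additional questions which can detect unhealthy use", and "A total score is calculated for each of the categories separately by adding the positive answers together". Section 6.6 also mentions a total score ("The total TAPS-score is used as"), but the sentence breaks off. Section 5.3 reports cut-offs of +1 and +2 per category from earlier work against the CIDI. The plan does not name them as the thresholds to be tested here.

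**The concern.** A cut-off chosen because it does well in a sample partly fits the chance features of that sample. Sensitivity and specificity read off at that cut-off in the same patients then look better, on average, than they will be in the next patients. The effect grows as the sample shrinks and as the score offers more cut-offs to choose from.

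The introduction presents the TAPS as a standard screener for mental health care. Overstated sensitivity would lead users to expect fewer missed cases than will occur.

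**Working it through.** **The plan's own figures.** Section 4.4: 100 new patients a year × 2.5 years = 250, and 250 × (1 − 0.40) = 150 eligible. Both reproduce. The required 40 has no derivation, so there is nothing to reproduce.

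**Inputs from the documents.** n = 40 and n = 100. A category score has one point for recent use plus one for each of two or three questions, so its maximum is 3 or 4 and there are 3 or 4 possible cut-offs.

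**Assumptions.**
- True AUC 0.78 to 0.90. This is the range quoted for the TAPS-1 in section 5.3 ("specificity = 0.80 and 0.85, AUC = 0.86 and 0.78, respectively" and "specificity = 0.85 and 0.91, AUC = 0.89 and 0.90, respectively"), which was found against substance use disorder, not MATE.
- Reference cases 20, 40 or 60%, from the dual-diagnosis range in section 1. The documents give no rate for MATE high severity.
- Eight cut-offs for a many-level score. The documents give no range for a total score.

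**Method.** The latent score is N(0,1) in non-cases and N(d,1) in cases, with d = √2 × Φ⁻¹(AUC). It is cut into levels. At cut-off c the true sensitivity is 1 − Φ(c − d) and the true specificity is Φ(c). In each simulated sample a rule picks the cut-off. The overstatement is the mean of (apparent sensitivity + specificity) − (true sensitivity + specificity) at that cut-off.

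**Results, in percentage points of the sum.**

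| Rule | 8 cut-offs, n=40 | 8 cut-offs, n=100 | 3 cut-offs, n=40 | 3 cut-offs, n=100 |
|---|---|---|---|---|
| Youden | 7.8 to 14.1 | 3.9 to 7.4 | 1.4 to 10.0 | 0.1 to 5.4 |
| Closest to corner | 5.6 to 10.5 | 2.3 to 4.6 | 0.1 to 7.1 | about 0 to 4.2 |
| Sensitivity at least 0.80 | 2.7 to 8.8 | 1.2 to 3.6 | 0.9 to 6.5 | 0.3 to 3.5 |
| Specificity at least 0.80 | 1.8 to 4.4 | 0.8 to 1.8 | – | – |
| Sensitivity closest to specificity | 1.2 to 2.3 | 0.3 to 1.1 | – | – |

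The three-cut-off columns cover three spacings of the cut-offs. Allowing for a fourth cut-off, the Youden range for a category score is about 1 to 10 points at n=40 and 0 to 6 at n=100. For the last two rules, a separate run with wider assumptions (AUC 0.75 or 0.85, 15 to 50% cases, 4 to 20 cut-offs) gave at most about 4 points at n=40 and 3 at n=100. In that run a cut-off fixed in advance gave −0.4 to +0.7 points, which is simulation noise. The overstatement therefore comes from the selection step.

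**Example** (Youden, 8 cut-offs, AUC 0.82, 40% cases).
- n=40: sensitivity 0.79 apparent against 0.73 true, specificity 0.76 against 0.72. Sum 1.55 − 1.45 = 0.10.
- n=100: 0.76 against 0.73, and 0.75 against 0.73. Sum 1.51 − 1.46 = 0.05.

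**Does the bootstrap help?** Same setting; sensitivity + specificity − 1 as apparent / true / corrected.
- n=40: 0.546 / 0.448 / 0.475. Bias 0.098 falls to 0.027, so (0.098 − 0.027)/0.098 = 72% is removed.
- n=100: 0.512 / 0.461 / 0.472. Bias 0.051 falls to 0.011.
- Across 20 to 60% cases at n=40, about 62 to 78% is removed.

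**Sampling error.** The exact 95% limits are the 0.025 quantile of Beta(x, m − x + 1) and the 0.975 quantile of Beta(x + 1, m − x), for x of m cases detected. With 40% cases, n=40 has 16 cases: 12 of 16 gives 0.48 to 0.93. n=100 has 40 cases: 30 of 40 gives 0.59 to 0.87.

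**The case against.** The strongest reply is that the plan never says accuracy will be reported at the derived cut-off, and section 6.6 ties sensitivity and specificity to items and combinations of items. That stands, so the point is conditional. The condition is nonetheless likely to be met: both measures need a threshold, and the analysis text provides for no other.

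Second, the size depends on choices the plan leaves open. That also stands. Some plausible rules carry little bias, the eight cut-offs are assumed, and with the documented category score at n=100 the effect can be almost nil. Forty is a floor, and section 4.4 expects about 150 eligible patients.

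Third, imprecision dominates. In the example sensitivity is inflated by 6 points at n=40, while its interval is 45 points wide (0.93 − 0.48). That is true, but a wide interval centred on an inflated estimate is still misplaced, and the correction costs little.

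A reader might infer more than the documents support:
- *The AUC is inflated too.* Choosing a cut-off does not change the AUC of a fixed score. It would matter only if items or combinations were also selected on the data.
- *Goal 2 has the same fault.* Goal 2 lists no ROC step.
- *The absence of follow-up shows that validation was ruled out.* Internal validation needs no follow-up, so that sentence shows only that there is no later wave of data.
- *The unfinished total-score sentence is an omission.* It may have been lost when the PDF was read, and it is not counted here.

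**Conclusion.** The point holds in conditional form and should be acted on. If sensitivity and specificity are reported at the ROC-derived cut-off in the patients who supplied it, their sum is overstated on average under accuracy-maximising rules, though not in every sample. With eight cut-offs and Youden, apparent exceeds true in 77 to 83% of samples at n=40 and 71 to 78% at n=100.

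Under Youden the size is about 8 to 14 points (n=40) and 4 to 7 (n=100) for a score with eight cut-offs, and about 1 to 10 and 0 to 6 for the category score. On the same AUC and case-rate grid, a minimum-specificity or balance rule gives about 0 to 4 and 0 to 2. These figures rest on the assumed AUC and case rates and on a binormal score. They leave out any search over item combinations, which would add to them. Confidence in the direction is good for accuracy-maximising rules; confidence in the size is moderate.

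**What to change.** In the goal 1 analysis text:

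1. Fix in advance the score entering the ROC (total or category), the reference outcome and the cut-off rule. For the reference, the analysis text speaks of degree of severity on the MATE while section 5.3 defines a binary high-severity variable; the latter is one workable choice. A bootstrap cannot repeat a selection whose rule or reference is undefined.
2. Report bootstrap optimism-corrected sensitivity and specificity with 95% CIs, repeating the cut-off selection in every resample. If items or combinations are selected on the data, repeat that step too and correct the AUC as well.
3. Label the derived cut-off exploratory.
4. Optionally, report sensitivity and specificity with exact 95% CIs at the existing +1 and +2 category cut-offs, with the mapping from categories to the patient-level MATE variable set beforehand. Note that the documents support these cut-offs against the CIDI, not against MATE.

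The cost is a few sentences and a short bootstrap program, with no extra data. The reported figures will be slightly less favourable. Under Youden some bias remains (about 1 to 5 points across the n=40 and n=100 settings checked, all with eight cut-offs and AUC 0.82), and the correction does nothing for imprecision.
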